7.6. Analysis of Exploratory Efficacy Variables

The following exploratory endpoints will be summarized by treatment group using the FAS:

- [REDACTED]
- [REDACTED]
- Summary of primary and contributing causes of death.
- Summary of donor chimerism.
- Summary of criteria and action taken for relapse of underlying disease.

7.7. Pharmacokinetic Analyses

A population PK analysis for itacitinib will be performed. Pharmacokinetic data from clinical Study INCB 39110-105 will be combined with data from this study, INCB 39110-301, and will aid in identification of the structural model and improve parameter estimation.

The population PK data preparation will be performed using SAS version 9.1 or later (SAS Institute Inc., Cary, NC). Exploratory data analyses and presentations of data will be performed using R version 3.2.0 or later (www.r-project.org), SPlus version 7.0 or later (Tobco Software Inc., Palo Alto, CA), and/or SAS version 9.1 or later. The PK analyses will use NONMEM version 7.1.0 or later (ICON Development Solutions, Dublin, Ireland) or Monolix version 2018R1 or later (Lixoft, Antony, France). The individual post hoc PK model parameters (CL/F, V/F, if applicable) will be determined and will be used to simulate individual exposures. Observed PK parameters such as C_{max} , t_{max} , and C_{min} will also be presented and summarized.

Simulation may be used to evaluate potential dose modifications if any covariates, for example, renal or hepatic impairment, are noted to have a clinically significant impact on exposure.

Additional details regarding this analysis may be found in the data analysis plan (DMB-18.155.1).

[REDACTED]

[REDACTED]

[REDACTED]

[REDACTED]

[REDACTED]

[REDACTED]

[REDACTED]

8. SAFETY AND TOLERABILITY

[Appendix B](#) provides a list of data displays.

8.1. General Considerations

All safety analyses will be conducted using the safety analysis set and summarized by actual treatment received on Day 1. Summary tables may be replaced with listings when appropriate. For instance, an AE frequency table may be replaced with a listing if it only contains a few unique PTs reported on relatively few subjects.

For summary analyses over time, analysis visits for laboratory assessments/vital signs/ECGs are defined in Section [4.1.5](#).

Listings will include all collected visits from the eCRF regardless of whether the visits are scheduled or unscheduled.

8.2. Adverse Events

8.2.1. Adverse Event Definitions

A TEAE in the treatment phase is either an AE reported for the first time or worsening of a pre-existing condition after first dose of itacitinib/placebo and before or at 30 days after last dose in the treatment phase. Analysis of AEs will be limited to TEAEs that occur during the treatment phase, but data listings will include all AEs, regardless of their timing with regard to study treatment administration.

A TEAE in the retreatment phase is either an AE reported for the first time or worsening of a pre-existing condition on or after Day 1 of retreatment with itacitinib. Treatment-emergent AEs in the retreatment phase will be listed.

Adverse events will be tabulated by MedDRA PT and SOC. Severity of AEs will be described and graded using the NCI CTCAE v4.03 ([NCI 2010](#)). The CTCAE reporting guidelines and grading details are available on the Cancer Therapy Evaluation Program website.

A grading (severity) scale is provided for each AE term. If the toxicity is not included in the CTCAE v4.03 criteria, then it will be rated on a scale of 1 to 5 as follows: 1 = mild, 2 = moderate, 3 = severe, 4 = life-threatening, and 5 = fatal. All toxicities will be graded based on the worst level reached, not the level they may have reached if they had not been treated. When the intensity of an AE changes over time for a reporting period (eg, between visits), then each change in intensity will be reported as an AE until the event resolves.

The subset of AEs considered by the investigator to be related to study drug will be considered to be treatment-related TEAEs. If the investigator does not specify the relationship of the AE to study drug, then the AE will be considered to be treatment-related. The incidence of TEAEs and treatment-related TEAEs will be tabulated. Serious TEAEs will also be tabulated.

Any missing onset date, causality, or severity must be queried for resolution. Unresolved missing values will be handled according to the following rules:

- An unresolved missing causality will be considered treatment-related.
- An unresolved missing severity will be identified as an unknown severity.

For purposes of analysis, all AEs will be considered TEAEs unless the AE can unequivocally be defined as not treatment-emergent.

8.2.2. Adverse Event Summaries

An overall summary of AEs in the treatment phase by treatment group will include the following:

- Number (%) of subjects reporting any TEAEs
- Number (%) of subjects reporting any serious TEAEs
- Number (%) of subjects reporting any Grade 3 or higher TEAEs
- Number (%) of subjects reporting any TEAEs related to itacitinib/placebo
- Number (%) of subjects reporting any TEAEs related to corticosteroids
- Number (%) of subjects who temporarily interrupted itacitinib/placebo because of TEAEs
- Number (%) of subjects with itacitinib/placebo dose reduction because of TEAEs
- Number (%) of subjects who permanently discontinued itacitinib/placebo because of TEAEs
- Number (%) of subjects who permanently discontinued itacitinib/placebo and corticosteroids because of TEAE
- Number (%) of subjects who had a fatal TEAE
- Number (%) of subjects who withdrew from the study because of a TEAE

Overall summaries of AEs (as described above) will also be provided by age group, sex, race, and region.

The following summaries will be produced for TEAEs occurring in the treatment phase by MedDRA term (if 10 or fewer subjects appear in a table, a listing may be appropriate):

- Number (%) of subjects reporting TEAEs by SOC and PT
- Number (%) of subjects reporting TEAEs by PT in decreasing order of frequency
- Number (%) of subjects reporting TEAEs by SOC, PT, and highest grade
- Number (%) of subjects reporting Grade 3 or higher TEAEs by SOC and PT
- Number (%) of subjects reporting Grade 3 or higher TEAEs by PT in decreasing order of frequency

- Number (%) of subjects reporting itacitinib/placebo treatment-related TEAEs by SOC and PT
- Number (%) of subjects reporting itacitinib/placebo treatment-related TEAEs by PT in decreasing order of frequency
- Number (%) of subjects reporting itacitinib/placebo treatment-related TEAEs by SOC, PT, and highest grade
- Number (%) of subjects reporting Grade 3 or higher itacitinib/placebo treatment-related TEAEs by SOC and PT
- Number (%) of subjects reporting fatal TEAEs by SOC and PT
- Number (%) of subjects reporting serious TEAEs by SOC and PT
- Number (%) of subjects with serious TEAEs by PT in decreasing order of frequency
- Number (%) of subjects reporting itacitinib/placebo treatment-related serious TEAEs by SOC and PT
- Number (%) of subjects reporting TEAEs leading to itacitinib/placebo dose interruption by SOC and PT
- Number (%) of subjects reporting TEAEs leading to itacitinib/placebo dose reduction by SOC and PT
- Number (%) of subjects reporting TEAEs leading to discontinuation of itacitinib/placebo by SOC and PT
- Number (%) of subjects reporting corticosteroid treatment-related TEAEs by SOC and PT
- Number (%) of subjects reporting corticosteroid treatment-related TEAEs by PT in decreasing order of frequency
- Number (%) of subjects reporting corticosteroid treatment-related TEAEs by SOC, PT, and highest grade
- Number (%) of subjects reporting corticosteroid treatment-related Grade 3 or higher TEAEs by SOC and PT
- Number (%) of subjects reporting corticosteroid treatment-related serious TEAEs by SOC and PT
- Number (%) of subjects reporting TEAEs leading to corticosteroid dose interruption by SOC and PT
- Number (%) of subjects reporting TEAEs leading to corticosteroid dose reduction by SOC and PT
- Number (%) of subjects reporting TEAEs leading to discontinuation of corticosteroids by SOC and PT
- Number (%) of subjects reporting TEAEs leading to withdrawal from the study by SOC and PT

The following summaries will be produced for TEAEs occurring in the treatment phase by MedDRA term based on baseline hepatic impairment status in combination with postbaseline azole usage:

- Number (%) of subjects reporting serious TEAEs by SOC and PT
- Number (%) of subjects reporting Grade 3 or higher TEAEs by SOC and PT
- Number (%) of subjects reporting fatal TEAEs by SOC and PT
- Number (%) of subjects reporting itacitinib/placebo treatment-related TEAEs by SOC and PT
- Number (%) of subjects reporting Grade 3 or higher thrombocytopenia TEAEs by SOC and PT based on customized MQ
- Number (%) of subjects reporting Grade 3 or higher neutropenia TEAEs by SOC and PT based on customized MQ
- Number (%) of subjects reporting Grade 3 or higher anemia TEAEs by SOC and PT based on customized MQ

Severity of hepatic impairment at baseline is defined as follows:

- Normal: Total bilirubin \leq ULN and AST \leq ULN
- Mild: Total bilirubin > 1.0 to $1.5 \times$ ULN and AST = any value or total bilirubin \leq ULN and AST $>$ ULN
- Moderate: Total bilirubin > 1.5 to $3 \times$ ULN and AST = any value
- Severe: Total bilirubin $> 3.0 \times$ ULN and AST = any value

If multiple azoles were used postbaseline, the most potent azole will be used for classification according to the following potency order (listed from strongest to weakest):

1. Ketoconazole
2. Itraconazole
3. Voriconazole
4. Posaconazole
5. Fluconazole

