### **7.4. Prior and Concomitant Medications**

Prior and concomitant medications will be reviewed to determine subject eligibility. All concomitant medications and measures must be recorded in the eCRF, and any medication received or procedure performed within 30 days before randomization and up to the safety follow-up visit will be recorded in the eCRF. The medication record will be maintained after signing the ICF to document concomitant medications, including any changes to the dose or regimen. Concomitant medications include any prescription, over-the-counter, or natural/herbal preparations taken or administered during the study period. Concomitant treatments and/or procedures that are required to manage a subject's medical condition during the study will also be recorded in the eCRF.

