4.2.4. Prior and Concomitant Medication

Prior medication is defined as any nonstudy medication taken within 30 days before the first dose of study drug.

Concomitant medication is defined as any nonstudy drug that is started accordingly:

- Before the date of first administration of study drug and is ongoing throughout the study or ends on/after the date of first study drug administration.
- On/after the date of first administration of study drug and is ongoing or ends during the course of study drug.

A prior medication could also be classified as "both prior and concomitant medication" if the end date is on or after first dose of study drug.

For the purposes of analysis, all medications will be considered concomitant medications unless the medications can unequivocally be defined as not concomitant.

The start/stop dates recorded in the eCRF by the investigator and his or her research staff will be used to identify when a concomitant medication was taken during the study. Unresolved missing start dates will be handled as follows:

- For the starting date, impute as follows:
 - If the day is missing, then impute as the first day of the month.
 - If the month is missing, then impute as the first day of the year.
 - If the year is missing, then the medication will be considered both prior and concomitant.
- For the ending date, impute as follows:
 - If the day is missing, then impute as the last day of the month.
 - If the month is missing, then impute as the last day of the year.

If the year is missing, then the medication will be considered as ongoing until the end of the study.

Note that the above imputation rules are for the purpose of defining prior and concomitant medications in the study. Imputed start/end dates are not saved in the analysis dataset.

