3.2.32	Summary of Itacitinib/Placebo Treatment-Related Treatment-Emergent Adverse Events in the Treatment Phase by MedDRA System Organ Class, Preferred Term, Hepatic Impairment Status at Baseline, and Postbaseline Azole Usage	Safety	X	X
3.2.33	Summary of Grades 3 or Higher Thrombocytopenia Treatment-Emergent Adverse Events in the Treatment Phase by MedDRA System Organ Class, Preferred Term, Hepatic Impairment Status at Baseline, and Postbaseline Azole Usage	Safety	X	X
3.2.34	Summary of Grades 3 or Higher Neutropenia Treatment-Emergent Adverse Events in the Treatment Phase by MedDRA System Organ Class, Preferred Term, Hepatic Impairment Status at Baseline, and Postbaseline Azole Usage	Safety	X	X
3.2.35	Summary of Grades 3 or Higher Anemia Treatment-Emergent Adverse Events in the Treatment Phase by MedDRA System Organ Class, Preferred Term, Hepatic Impairment Status at Baseline, and Postbaseline Azole Usage	Safety	X	X

Table No.	Title	Population	Standard	In-Text
Labs, Vital Signs, and ECGs				
3.3.1	Summary of Laboratory Values – Hematology	Safety	X	X
3.3.2	Shift Summary of Hematology Values – to the Worst Abnormal Value	Safety	X	X
3.3.3	Shift Summary of Hematology Laboratory Values in CTC Grade – to the Worst Abnormal Value	Safety	X	X
3.3.4	Summary of Laboratory Values – Chemistry	Safety	X	X
3.3.5	Shift Summary of Chemistry Values – to the Worst Abnormal Value	Safety	X	X
3.3.6	Shift Summary of Chemistry Laboratory Values in CTC Grade – to the Worst Abnormal Value	Safety	X	X
3.4.1	Summary of Systolic Blood Pressure	Safety	X	
3.4.2	Summary of Diastolic Blood Pressure	Safety	X	
3.4.3	Summary of Pulse	Safety	X	
3.4.4	Summary of Respiratory Rate	Safety	X	
3.4.5	Summary of Body Temperature	Safety	X	
3.4.6	Summary of Body Weight	Safety	X	
3.4.7	Summary of QRS Interval (ms) From 12-Lead ECG	Safety	X	
3.4.8	Summary of QT Interval (ms) From 12-Lead ECG	Safety	X	
3.4.9	Summary of QTcB Interval (ms) From 12-Lead ECG	Safety	X	
3.4.10	Summary of QTcF Interval (ms) From 12-Lead ECG	Safety	X	
3.4.11	Summary of RR Interval (ms) From 12-Lead ECG	Safety	X	
3.4.12	Summary of PR Interval (ms) From 12-Lead ECG	Safety	X	
3.4.13	Summary of Clinically Significant ECG Abnormalities	Safety	X	

Listings

Listing No.	Title
2.1.1	Subject Disposition Status
2.1.2	Subject Enrollment and Site Information
2.1.3	Subject Retreatment Disposition Status
2.2.1	Protocol Deviations
2.2.2	Randomized Subjects With Inclusion/Exclusion Criteria Violations
2.3	Analysis Populations

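### SAP 8.2.2 groups adverse events by the strongest azole ever used after baseline, ignoring event timing; this biases azole comparisons within an arm and dilutes a real interaction between arms

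*SAP*

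**What the plan says.** SAP 8.2.2 plans seven summaries of treatment-phase TEAEs: serious, Grade 3 or higher, fatal, treatment-related, and Grade 3 or higher thrombocytopenia, neutropenia and anemia. They are grouped "based on baseline hepatic impairment status in combination with postbaseline azole usage". For a subject with more than one azole the rule is: "If multiple azoles were used postbaseline, the most potent azole will be used for classification". The potency ranking runs from ketoconazole down to fluconazole. The titles in SAP Appendix B, such as Table 3.2.34 ("Summary of Grades 3 or Higher Neutropenia Treatment-Emergent Adverse Events in the Treatment Phase"), add no timing condition.

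SAP 8.2.1 counts events that begin or worsen "after first dose of itacitinib/placebo and before or at 30 days after last dose in the treatment phase". Protocol 7.4 sets the medication window: "any medication received or procedure performed within 30 days before randomization and up to the safety follow-up visit will be recorded in the eCRF". An azole begun late, or after study drug has stopped, can therefore set the label.

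Dates are available. SAP 4.2.4 says that the medication dates entered by the sites "will be used to identify when a concomitant medication was taken during the study". SAP 5.3.4 and 8.1 present safety output by actual treatment group.

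**The concern.** The sentence on multiple azoles is only a tie-break. The ever-used-after-baseline reading comes from the grouping label together with the absence of any rule, in either document, that the azole must start before the event, overlap study drug or last a minimum time. On that reading each subject carries one fixed label that may be set after the event it is meant to explain.

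Three distortions follow.

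- **Reverse order.** Azoles are antifungals, so neutropenia or infection may prompt one. Grade 3 neutropenia on Day 10 followed by voriconazole on Day 20 is tabulated as neutropenia in a voriconazole user.
- **Upward reassignment.** An event on fluconazole moves to voriconazole if voriconazole is used later.
- **Immortal time.** In the fatal table the event cannot precede the azole, but early deaths fall into the no-azole group because those subjects never had time to start one.

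Protocol 1.5 reports a nearly 5-fold exposure increase with itraconazole, and in the legible SAP these are the only adverse-event tables that address azole use. A false pattern could mislead a reader, and a real one could be blurred.

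**Working it through.** The plan gives no figure to reproduce. The check is a model with no true azole effect.

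**Assumptions (none from the documents).** 25% of subjects have the event by Day 180; 30% of those not on an azole at Day 1 would start one by Day 180 if event-free; an event multiplies the azole-start rate by k. Hazards are constant and follow-up is 180 days. Write L = −ln(0.75) = 0.2877 and a = −ln(0.70) = 0.3567.

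**Nonfatal events, nobody on an azole at Day 1.**
- Never azole, no event: 0.75 × 0.70 = 0.525.
- Never azole, event: L·e^(−ka)·(1 − e^(−x))/x, with x = L + a − ka. For k = 3 this is 0.1230.
- Risk without azole: 0.1230/(0.1230 + 0.525) = 0.190.
- Risk with azole: (0.25 − 0.1230)/(1 − 0.648) = 0.1270/0.3520 = 0.361.
- Risk ratio: 0.361/0.190 = 1.90, where the truth is 1.0.

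The same formula gives 1.00, 1.45 and 2.83 for k = 1, 2 and 5. Simulated runs at k = 5 gave 2.83 to 2.89.

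**With a share b on an azole at Day 1,** the azole-group risk becomes [0.25b + 0.1270(1 − b)]/[b + 0.3520(1 − b)] for k = 3. At b = 0.30 this is 0.1639/0.5464 = 0.300, so the ratio is 1.58. For k = 2 and 5 it is 1.28 and 2.24.

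Over these six settings (k = 2, 3, 5; b = 0 or 0.30), 31% to 76% of azole-group subjects with an event had it before the azole. Classing by onset returned rate ratios of 0.99 to 1.01.

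**Fatal events.** For a death risk d by Day 180, l = −ln(1 − d) and deaths before any azole are l/(l + a) × [1 − 0.70(1 − d)]. For d = 0.20 this is 0.3849 × 0.44 = 0.1693.
- Risk without azole: 0.1693/(0.1693 + 0.56) = 0.232.
- Risk with azole: (0.20 − 0.1693)/0.2707 = 0.113.
- Risk ratio: 0.49.

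For d = 0.33 it is 0.52. With 30% on an azole at Day 1 the two ratios are 0.72 and 0.75.

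**A second set of assumptions.** Mean treatment of 90 days (cap 180) plus a 30-day tail; 50% with a Grade 3 or higher event, or 15% with a fatal event, by Day 90; 20% or 40% new azole starts by Day 90; 0% or 40% on an azole at Day 1; k = 1 or 3 (nonfatal). With no true effect, nonfatal ratios were 1.10 to 2.14 and fatal ratios 0.62 to 0.86. A true fatal hazard ratio of 1.5 appeared as 0.89 to 1.24. The time-ordered split gave 0.99 to 1.01 when the truth was 1.0 and 1.49 to 1.52 when it was 1.5.

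**Comparison between arms within an azole class (first model).** With no interaction the itacitinib-placebo ratio stayed at 0.99 to 1.02. Now let the on-azole event hazard double in the itacitinib arm only, with k = 3 and nobody on an azole at Day 1:
- The share event-free after starting an azole is a·e^(−2L)·(1 − e^(−(a−L)))/(a − L) = 0.1939.
- Events among azole users are 1 − 0.525 − 0.1939 − 0.1230 = 0.1581, against 0.1270 on placebo.
- The azole group is the same size in both arms, so the arm ratio is 0.1581/0.1270 = 1.25.

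Over k = 1 to 5 and 0% to 60% on an azole at Day 1, the arm ratio was 1.20 to 1.70. Rates classed by onset gave 1.98 to 2.02.

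Part of that gap is scale. At a 25% risk, a doubled hazard gives a risk ratio of (1 − 0.75²)/0.25 = 0.4375/0.25 = 1.75 even with perfect classification. The loss from the grouping itself is from 1.75 down to 1.20 to 1.70.

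**The case against.** The strongest reply is the placebo arm. SAP 5.3.4 and 8.1 put itacitinib and placebo side by side within each azole class. Placebo subjects have no itacitinib exposure for an azole to raise, and both arms carry the same ordering errors. This largely stands against a false signal. It weakens if the arms start azoles differently after events: when one arm's post-event start rate was 1.5 times the other's, arm ratios moved to 1.04 to 1.07 (azole) and 0.83 to 0.93 (no azole) with no true effect. It does not prevent dilution.

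A reader might infer that the tables will show azoles tripling cytopenias or halving deaths. The documents do not support this. The near-threefold figure needs k = 5, and both figures need nobody on an azole at Day 1, while Protocol 5.2.4 treats anti-infective prophylaxis as routine and lets it continue. No value of k is documented, and the 20% and 33% death risks resemble the planning rates for nonrelapse mortality, not rates of fatal TEAEs.

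A reader might also infer that the sponsor will take dose advice from these tables. Nothing says so. Protocol 1.5 and 5.5.4.2 already carry advice based on a healthy-volunteer study and a PBPK model, and SAP 7.7 leaves further dose evaluation to PK simulation. That the tables serve to examine interactions is itself an inference from the potency order.

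Two limits on the remedy also stand. Classing by onset does not remove confounding by indication, since sicker subjects start azoles; the near-perfect recovery above comes from a model without a confounder. Cells also become thin: six azole classes (five plus none) × four hepatic classes × two arms is 48 cells for about 436 subjects.

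**Conclusion.** The classification is defective as written, with limited consequences. Azole-versus-no-azole comparisons within an arm are biased: with no true effect, nonfatal risk ratios run from about 1.0 to between 2.8 and 2.9, and fatal ones from about 0.5 to 0.9. Where in those ranges the trial would fall depends on azole-start rates, the effect of an event on azole start, and the share on azoles at Day 1, all of which are assumed. Nonfatal bias can vanish if events do not prompt azoles and follow-up is equal; the immortal-time bias in the fatal table remains unless all azole use begins by Day 1.

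The itacitinib-placebo contrast within an azole class is largely protected from a false signal when both arms start azoles alike, but a doubled on-azole hazard shows as about 1.2 to 1.7. The tables are descriptive and do not touch the primary or key secondary analyses. The change is worth making because the dates already exist, not because a trial conclusion depends on it.

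**What to change.** In SAP 8.2.2:

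1. Count a TEAE under an azole only if its onset is on or after that azole's start and no later than a prespecified interval after its stop.
2. Apply the potency order only to azoles taken at the same time.
3. Show exposure-adjusted rates for on- and off-azole time by treatment arm, collapsing azole or hepatic classes where cells are sparse. Name the itacitinib-placebo contrast within on-azole time as the main reading.
4. Add the same tables by azole ongoing on Day 1, a label that no later event can alter.
5. State how partial azole dates are used. SAP 4.2.4 moves a start with a missing day to the first of the month, which can place an azole before an event it followed, and it does not save imputed dates in the analysis dataset.

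The cost is SAP wording, programming and smaller cells. No new data are needed: medication dates are collected, and SAP 8.2.1 already requires missing onset dates to be queried. Confounding by indication remains and should be acknowledged beside the tables.
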